Aim 3. To examine the effects of acquisition of intestinal nematodes during childhood and of regular mass treatment in childhood. *After one year of age, children will be randomised to receive albendazole or placebo every 3 months. Both groups will receive annual, selective treatment based on stool analysis.* Prior helminth infection is associated with impaired responses to immunisation, but it is not certain whether acquisition of helminths leads to loss of an established response, or increased susceptibility to bacterial and viral infections, and whether this can be prevented by regular de-worming. This will be determined by comparing children who receive regular de-worming as well as annual, selective treatment with those who receive annual, selective treatment only (groups C1 vs C2, appendix 4). Prevention of helminth infections may have disadvantages, such as increased risk of severe malaria and thus, for our objectives, a randomised trial is appropriate. Other considerations are as follows. Regular de-worming may have benefits for growth and cognitive performance in childhood, but a recent meta-analysis has shown that the evidence, particularly relating to cognitive performance, is still inconclusive. Again, these outcomes are not the main issue for this study, but will be recorded.

**Aim 4.** To examine the effects of childhood schistosomiasis. This component will be observational because the incidence of schistosomiasis in children under 5 is not expected to be high enough to justify mass treatment. As in the case of intestinal nematodes, we wish to investigate whether acquisition of helminths leads to loss of an established response to immunisations, and influences susceptibility to other infections. For this observational component, important potential nutritional and environmental confounding factors for the effects of helminths are known to exist. These will be recorded and appropriate adjustments will be made.

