#### Sample size estimates

The cohort size of 2500 was proposed, based on clinical outcomes, for 80% power to detect statistically significant differences (P<0.05) between the children of mothers treated with albendazole or placebo during pregnancy; or for children randomised at one year of age to

albendazole vs placebo every three months. The change in design to include comparison of treatment with praziquantel or placebo during pregnancy has implications for the sample size required. The incidence of ALRI in children under five is expected to be above 10 per 100 person years (pyr); diarrhoea over 100 per 100pyr; clinical malaria, about 100 per 100 pyr. For these common outcomes, and for effects which are expected to be large, such as the effect on cytokine production in the whole blood assay, the proposed cohort is likely to be large enough to accommodate the change in design.

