Our initial objective was to establish a cohort that would be sufficiently large to allow analysis of the effects of helminths and their treatment of the incidence of tuberculosis. For this there are, at present, insufficient data to make accurate calculations regarding the sample size required. The incidence of *tuberculosis* in children under five in Entebbe is not known. In a well-documented community in South Africa the incidence in children aged 0-5 years was 3588/100.000 p.a.; 3.5 times the incidence in adults. The estimated overall incidence in Uganda is 320/100,000 p.a. so a figure of 500/100,000 p.a. for children under 5 may be reasonable (Appendix 2C)). A study with 1170 children in each arm and median follow up of 3 years would detect a difference in incidence of 250/100,000 to 750/100,000 cases p.a. between two equal groups (e.g. children of mothers treated with albendazole vs children of mothers treated with placebo). This estimate of effect is large but, if helminths are crucial to the reduced effectiveness of BCG in tropical environments, a large effect is expected. On the other hand, the change in design to include an additional intervention means that the required sample size is likely to be even larger. We therefore propose to review the findings when the study has been running for approximately 18 months. Data regarding the impact of interventions in the mothers on incidence of infectious diseases in the first year of life and on immune responses to tuberculosis antigens one year after BCG immunisation will assist in further planning (appendix 9).

Protocol amendment, January 2009. For *TB infection* among five year olds, where the overall prevalence is expected to be about 15%, the study will have over 90% power, with p<0.05, to detect a difference of 10% vs 20% between either of the interventions in pregnancy, or between the intervention arms in childhood.

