#### **CHILDREN**

At One Year Follow-Up Children will be randomised to receive routine albendazole every 3 months or placebo, starting at 15 months. All will receive annual selective treatment based on stool examination.						
Group C1	Group C2					
Albendazole every 3 months and annual	Placebo every 3 months and annual					
selective treatment.	selective treatment.					

Annual Follow-Up Visits to Age 5 Years	
Helminths present, treated	Helminths absent

The analysis for the effect of maternal intestinal nematode infection will compare groups according to the presence or absence of intestinal nematodes at the antenatal visit, and whether or not they were treated; i.e. outcomes will be compared for children of mothers in groups G1-2-5-6 (intestinal nematodes, treated), G3-4-7-8 (intestinal nematodes, not treated), G9-10-13-14 (no intestinal nematodes, treated) G11-12-15-16 (no intestinal nematodes, not treated). The findings will be adjusted for the presence or absence of schistosomiasis, treatment with praziquantel, and the presence or absence of helminths at delivery. The overall effect of albendazole treatment during pregnancy will be determined by comparing G1-2-5-6-9-10-13-14 vs G3-4-7-8-11-12-15-16.

[figure not shown]
The analysis for the effect of maternal schistosomiasis will compare groups according to the presence or absence of schistosomiasis at the antenatal visit, and whether or not they were treated; i.e. outcomes will be compared for children of mothers in groups G1-3-9-11 (schistosomiasis, treated), G2-4-10-12 (schistosomiasis, not treated), G5-7-13-15 (no schistosomiasis, treated) G6-8-14-16 (no schistosomiasis, not treated). The findings will be adjusted for the presence or absence of intestinal nematodes, treatment with albendazole, and the presence or absence of helminths at delivery. The overall effect of praziquantel treatment during pregnancy will be determined by comparing G1-3-5-7-9-11-13-15 vs G2-4-6-8-10-12-14-16.

The analysis for the effect of intestinal nematodes in children will compare groups according to whether they receive routine albendazole every 3 months or annual selective treatment; i.e. outcomes for children in groups C1 and C2 will be compared. The presence or absence of helminths at annual follow up visits will be taken into account.

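### The randomised child comparison (C1 vs C2) is labelled as the effect of acquiring intestinal nematodes, but it estimates only what three-monthly albendazole adds to annual stool-based treatment

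*Protocol*

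**What the plan says.** Aim 3 (protocol, Specific Aim) has two parts: the effect of acquiring intestinal nematodes in childhood, and the effect of regular mass treatment. Under Interventions and exposures, the Aim 3 text explains why the first part is open: "it is not certain whether acquisition of helminths leads to loss of an established response". It then asks whether such an effect could be prevented by regular de-worming, and continues: "This will be determined by comparing children who receive regular de-worming as well as annual, selective treatment with those who receive annual, selective treatment only". So one comparison is to settle both parts.

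Appendix 4 (Plan for Analysis, Children) gives that comparison a single label: "The analysis for the effect of intestinal nematodes in children will compare groups according to whether they receive routine albendazole every 3 months". The rest of the sentence sets this against annual selective treatment, joined by the word *or*. The table above it gives annual selective treatment to both C1 and C2. Appendix 4 adds that helminth status at annual visits will be taken into account, without saying how.

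Sample size estimates describes the child comparison as "albendazole vs placebo every three months". For TB infection it claims over 90% power for 10% versus 20%, for the pregnancy interventions "or between the intervention arms in childhood".

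**The concern.** A comparison can carry a conclusion about nematode acquisition only to the extent that the two arms differ in nematode exposure. Here the control arm is not left untreated. Infections found at the annual visit are treated in both arms, so C2 carries mainly infections acquired since the last visit, plus those the stool examination missed or treatment failed to clear.

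The label matters most if the result is null. Read under the Appendix 4 label, no difference between C1 and C2 would say that nematodes do not affect vaccine responses or disease in children. What it would show is that more frequent albendazole adds nothing detectable to annual test-and-treat. These are different conclusions with different policy consequences.

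Taking annual helminth status into account does not repair this. That status is measured after randomisation, is affected by the allocated treatment, and lies on the path from treatment to outcome. Conditioning on it would weaken the randomised comparison without producing a randomised estimate of the effect of acquisition.

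**Working it through.** **1. The sections side by side**

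| Place in protocol | C1 | C2 | Question attached |
|---|---|---|---|
| Interventions and exposures, Aim 3 | three-monthly albendazole plus annual selective | annual selective only | acquisition, and prevention by de-worming |
| Appendix 4, table | three-monthly albendazole plus annual selective | three-monthly placebo plus annual selective | none stated |
| Appendix 4, text | three-monthly albendazole | *or* annual selective | effect of intestinal nematodes |
| Ethical Considerations | mass treatment | annual selective | none stated |

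The first two rows agree on the arms. The Appendix 4 text departs from its own table on C1, and its label names a question that the arms address only in part.

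**2. The stated power**

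Inputs: 10% versus 20% and P<0.05 (Sample size estimates), and about 830 children (Assessment of TB infection in 5-6 year olds), taken as 415 per arm. The test is taken as two-sided.

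- Standard error under the null: √(2 × 0.15 × 0.85 / 415) = 0.0248
- Standard error under the alternative: √((0.10 × 0.90 + 0.20 × 0.80) / 415) = 0.0245
- z = (0.10 − 1.96 × 0.0248) / 0.0245 = 2.09, so power is 98%

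This agrees with the claim of over 90%.

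**3. How much of the exposure contrast remains**

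The protocol gives no childhood nematode incidence, cure rate or clearance rate, so this step shows a range under assumptions.

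Model: children are uninfected at 15 months and followed to 5 years (3.75 years), with constant acquisition rate λ. With full cure and no natural clearance, the mean share of time infected over an interval T that starts free of infection is

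1 − (1 − e^(−λT)) / (λT).

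Example with λ = 0.2 per year:

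- Never treated, T = 3.75: 1 − (1 − e^(−0.75)) / 0.75 = 29.6%
- Annual treatment at 24, 36 and 48 months, all infections found: 7.1% over the first 0.75 year and 9.4% over each later year, so (0.75 × 7.1 + 3 × 9.4) / 3.75 = 8.9%
- Three-monthly treatment, T = 0.25: 2.5%

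Retained contrast = (annual − three-monthly) / (untreated − three-monthly) = (8.9 − 2.5) / (29.6 − 2.5) = 24%.

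If one stool finds 60% of infections, infected time in C2 is 14.9% and the retained contrast is (14.9 − 2.5) / (29.6 − 2.5) = 46%. The 60% is the protocol's figure for maternal schistosomiasis (Ethical Considerations), used here only as one end of a range.

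Retained contrast for λ from 0.05 to 0.4 per year:

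| Cure and natural clearance (assumed) | All infections found | 60% found |
|---|---|---|
| 100% cure, no clearance | 21–28% | 43–50% |
| 70% cure, clearance 0.5 per year | 42–48% | 62–66% |

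The second row applies the same schedule with partial cure at each treatment and infections also lost at 0.5 per year.

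**The case against.** The strongest reply is that nothing is concealed. The Aim 3 text gives the actual contrast, Ethical Considerations calls it mass versus annual selective treatment, and the Appendix 4 table shows annual treatment in both arms. C1 versus C2 answers the mass-treatment half of Aim 3 directly. An analysis by infection status is also foreseen: Outcome (3) says the effect of childhood helminth infection on disease will be examined in the whole cohort. All of this stands. It narrows the point to the acquisition conclusion attached to the comparison and to the label in Appendix 4.

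Two stronger readings are tempting.

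- *The child comparison is underpowered.* If 10% versus 20% were the effect of nematodes left untreated, and only half or a quarter of the excess survived annual treatment, power at 415 per arm would be 59% (10% versus 15%) or 21% (10% versus 12.5%). The protocol states no such premise. It gives 10% versus 20% as a difference between the childhood arms, and those arms already include annual treatment.
- *C1 versus C2 cannot inform on acquisition at all.* This goes too far. C2 children can carry infection between annual visits, and for longer if a stool result is falsely negative, so the contrast is reduced and not abolished.

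The dilution figures are also sensitive to their assumptions. Allowing imperfect cure and natural clearance raises the retained contrast materially, as the second row of the table shows.

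**Conclusion.** The point holds as one of definition and interpretation. C1 versus C2 estimates the effect of adding three-monthly albendazole to annual selective treatment. As a test of nematode acquisition it is diluted and asymmetric: a difference would be evidence about nematodes, but the absence of one would not be evidence that they have no effect.

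The size of the dilution cannot be derived from the documents. The range of about 20% to 65% retained rests wholly on the assumed acquisition, cure, clearance and detection values, and should be read as an illustration. The stated power for the childhood arms is arithmetically sound and needs no correction.

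**What to change.** 1. In Interventions and exposures (Aim 3) and in Appendix 4, define C1 versus C2 as three-monthly albendazole plus annual selective treatment versus annual selective treatment only. Limit its conclusion to that contrast.
2. In Appendix 4, reconcile the *or* in the text with the table, which gives annual selective treatment to both groups.
3. Do not condition the randomised comparison on helminth status at annual visits.
4. Report the effect of nematode acquisition as a separately labelled observational analysis, building on the general intention in Outcome (3). Use each annual stool result, before that visit's treatment, as a time-varying exposure. Adjust for nutritional and environmental confounders of the kind already planned for Aim 4.

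The cost is rewording plus one analysis of data already collected. The price is that the acquisition conclusion becomes observational. No change to treatment is proposed.

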#### Children: follow up visits.

A clinic at which mothers and children can be seen for follow up will be established in the renovated building at the Private Wing. Children will be seen there at scheduled follow up visits, or if they are sick.

Children will be seen routinely at their immunisation visits (6, 10 and 14 weeks) and then every three months up to the age of 18 months. This will allow their immunisations to be documented (at 6, 10 and 14 weeks, and then measles immunisation at 9 months) and their weight to be recorded. At first this will be done at the study clinic. Later it may be possible to devolve some of these visits to community clinics nearer to the mothers' homes. At one year mothers will be asked to give informed consent on behalf of the children for participation in the randomised, placebo controlled trial of three-monthly albendazole treatment. At 15 and 18 months they will receive their first two doses of albendazole or placebo. At 18 months blood samples will be obtained from children of HIV-positive mothers to ascertain the child's HIV status.

At routine annual follow up visits clinical data, blood for full blood count, malaria slide and immunological studies (2-5 ml) and stool samples will be obtained. Children found to have helminths in stool samples collected at annual visits will be treated by the field workers.

Protocol amendment, January 2009. At five years, 10 ml will be obtained to accommodate assessment of TB infection by T-spot.TB® assay and assessment of additional immune responses in children who were exposed to schistosomiasis in utero. At six years, 5 ml will be obtained for a T-spot.TB® assay.

Protocol amendment, January 2009. For more detailed assessment of schistosomiasis infection at the age of five years in children who were exposed to schistosomiasis in utero, three stool samples will be obtained from this subgroup of five year olds.

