We will use whole blood assays and antibody assays in all members of the cohort to evaluate the effect of helminths, and their treatment, on the development and maintenance of responses to BCG and tetanus immunisation. Whole blood assays can be used in large numbers of subjects and require small amounts of blood. They measure responses biased towards CD4+ T-cell, or nonspecific responses (monocyte, NK-cell, eosinophil or basophil). Mycobacterial antigens, tetanus toxoid and the mitogen phytohaemagglutinin (PHA) will be used for stimulation. The mycobacterial antigens will be whole cell lysate or culture filtrate proteins of *M. tuberculosis*, which are homologous between *M. tuberculosis* and *M. bovis* BCG, and early secreted antigen of *M. tuberculosis* (ESAT-6), which is specific for *M. tuberculosis*, to distinguish responses to immunisation and *M. tuberculosis* infection. We will measure the "type 1" cytokines, IFN- $\gamma$  and IL-2. Our results suggest that discrepancies between these two responses may be of particular interest: in HIV-1 positive adults, IL-2, but not IFN- $\gamma$ , responses were associated with increased risk of active tuberculosis; and IL-2 responses increased, while IFN- $\gamma$  responses declined, after treatment of schistosomiasis (Appendix 1, Figure 3). We will now determine whether helminth exposure has a differential effect on these two responses following immunisation. For "type 2" responses, IL-4 is seldom detectable in these assays in response to *M. tuberculosis* antigens, so we will measure IL-5 and IL-13 to examine whether helminths promote type 2 responses following immunisation. In mothers with schistosomiasis and their children, responses to vaccine antigens and to Schistosoma antigens will be compared, and we will also measure IL-10 and TGF- $\beta$  responses, to examine whether helminth-induced immunosuppressive cytokines have a role in helminth associated effects. Antibody responses can also be studied in large numbers of subjects. Our existing assays for mycobacterial antibodies and their subclasses will be extended to tetanus. If helminths promote type 2 responses to unrelated antigens we expect a predominance of IgG4 and IgE subclasses following immunisation.

We will use ELIspot assays to evaluate the effect of helminths, and their treatment, on CD8+ T-cell responses following BCG and measles immunisation. Approximately 30% of Ugandans possess

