#### APPENDIX 3: The impact of helminths on the response to immunisation and on susceptibility to infectious diseases in childhood in Uganda. Proposed Study Profile.

First visit to the antenatal clinic.

• Women who live in study area; no history of adverse effects of anti-helminthics.

Т

- Consent to study of treatment in pregnancy.
- Screening investigations, including Hb, HIV, RPR, immunological studies.
- Provision of antimalarials and haematinics.
- Request stool sample.

	↓
On receipt of stool sample; gestation > 14	weeks; screening Hb results available.

 
Severe anaemia:
 
Treat with albendazole; exclude
 
Persistent diarrhoea with blood:
 
investigate and treat; exclude
 
	
 
Not severe anaemia:
 
Randomise to albendazole or placebo & praziquantel or placebo
 

At delivery.	

 
Mother:
 
Blood and stool samples
 
Nevirapine if known HIV+
 
	

Child:

Cord blood

Nevirapine if mother known HIV+

Post delivery.	↓
• Mass treatment with albendazole and praziquantel; selective treatment for Strongyloides .	• 1-2 samples post immunisation for studies of time course of immune response in selected participants.
	 ▼
	At one year.
	
 
Blood and stool samples
 
Specific treatment for worms found
 
Consent to study of treatment in childhood.
 
Randomisation to receive albendazole or placebo at 3 month intervals, starting at age 15 months
 

	Annual visits.
	Blood and stool

- Blood and stool
- Specific treatment for worms found

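### The randomised comparison of three-monthly albendazole in children names no pre-randomisation covariate, although one-year immune responses and first-year illness counts are collected; the cost is precision only

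*Protocol*

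**What the plan says.** Appendix 4 (Plan for Analysis) sets adjustment comparison by comparison. The two maternal analyses each carry a list: the other class of worm, the other study drug, and helminths at delivery. For the children it says that "outcomes for children in groups C1 and C2 will be compared", and then only that "The presence or absence of helminths at annual follow up visits will be taken into account".

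The data that could serve as baseline are described elsewhere in the protocol:

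- Under Children: follow up visits, annual visits include "blood for full blood count, malaria slide and immunological studies (2-5 ml) and stool samples will be obtained".
- Under Principal Outcomes, Outcome (1): "We will use whole blood assays and antibody assays in all members of the cohort to evaluate the effect of helminths", with BCG and tetanus as the responses studied.
- Appendix 3, in the one-year box, lists blood and stool samples and then "Randomisation to receive albendazole or placebo at 3 month intervals, starting at age 15 months".
- Under Children: interim disease events, field workers record illness every two weeks.
- Appendix 9, main study analysis (b), plans to analyse one-year immune responses and first-year malaria, diarrhoea and pneumonia (ALRI), so these values are meant to be assayed and tabulated, not just stored.

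Under Interventions and exposures, Aim 3 starts from the statement that "it is not certain whether acquisition of helminths leads to loss of an established response" and continues: "This will be determined by comparing children who receive regular de-worming as well as annual, selective treatment with those who receive annual, selective treatment only".

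**The concern.** A child's response to BCG or tetanus antigen at ages two to five probably depends in part on that child's response at age one, and a child with many malaria or diarrhoea episodes in the first year probably goes on to have more. Both are known before any study dose is given in childhood. Adjusting for such a variable in a randomised comparison removes between-child variation from the error term and leaves the estimated effect unchanged in expectation. The children's paragraph of Appendix 4 names one covariate, and it is observed after randomisation. It names none of the baseline values.

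At stake is the width of the confidence intervals for the Aim 3 effects. The protocol itself says, under Sample size estimates, that adding the praziquantel comparison is likely to increase the sample size needed for tuberculosis, so precision that costs no extra data is worth having where it can be had.

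**Working it through.** **The plan's own figure.** Sample size estimates gives 1170 children per arm to detect tuberculosis incidence of 250 versus 750 per 100,000 per year over 3 years. As three-year risks these are 0.0075 and 0.0225. The usual two-proportion formula (two-sided 5%, 80% power) gives 1030 per arm. With continuity correction this is (1030/4) × [1 + √(1 + 4/(1030 × 0.015))]² = 1160, within 1% of 1170. The stated figure is sound, and nothing below disputes it.

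**Immune responses.** The protocol gives no correlation ρ between the one-year and later response, so 0.3, 0.5 and 0.7 are assumed. Analysis of covariance multiplies the variance by 1 − ρ²:

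- ρ = 0.3: 0.91
- ρ = 0.5: 0.75, equivalent to 1/0.75 = 1.33 times as many children
- ρ = 0.7: 0.51

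For an effect with 80% unadjusted power, adjusted power is Φ(2.80/√(1 − ρ²) − 1.96) = 84%, 90% and 97.5%.

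The detectable difference is 2.80 × √(2/n) SD, times √(1 − ρ²) after adjustment:

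- n = 415 per arm (half of the roughly 830 five-to-six-year-olds in the 2009 tuberculosis amendment): 0.195 SD falls to 0.186, 0.168 or 0.139 SD
- n = 1170 per arm: 0.116 SD falls to 0.111, 0.100 or 0.083 SD

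**Choice of adjustment.** A raw change score has variance factor 2(1 − ρ) = 1.4, 1.0 and 0.6, giving power of 66%, 80% and 95%. Below ρ = 0.5 it is worse than no adjustment.

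**Does the unadjusted contrast answer the Aim 3 question?** Randomisation gives both arms the same expected one-year response, so the expected difference at follow-up equals the expected difference in change. In 4000 simulated trials (415 per arm, true effect 0.20 SD, ρ = 0.5) the follow-up-only, change-score and covariance estimates each averaged 0.201. Their relative variances were 1.00, 1.00 and 0.76.

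**Illness counts.** Assume Poisson episodes with gamma-distributed child-level variation of variance k, a constant rate, one baseline year (mean μ₁) and 3.75 follow-up years from 15 months to age five (mean μ₂). Then ρ² = k²μ₁μ₂ / [(1 + kμ₁)(1 + kμ₂)].

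- Malaria and diarrhoea, about 1 episode per year (Sample size estimates): k = 0.25, 0.5, 1.0 gives ρ² = 0.10, 0.22, 0.39, variance factors 0.90, 0.78, 0.61 and power 84%, 89%, 95%.
- Pneumonia, 0.1 per year: variance factors 0.998, 0.99, 0.975, a gain of about one point of power at most.
- Tuberculosis, 0.005 per year: even at k = 1, ρ² = 0.005 × 0.01875 / (1.005 × 1.01875) ≈ 0.0001, in effect nothing.

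**The case against.** The strongest reply is that a protocol defines the contrast and leaves covariates, transformations and rate models to a statistical analysis plan, which is not available here. Appendix 6 also says that plans for the later years will follow from earlier analyses. This stands in part: the text does not forbid a baseline covariate, and a reader who infers that the plan excludes one goes beyond it. But Appendix 4 does choose adjustment variables for each comparison, and for the children its choice is a post-randomisation one. The point is therefore about a choice the document makes.

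A reader might also infer that, without the one-year value, the comparison cannot measure loss of a response. The documents do not support this. Aim 3 is to be answered by comparing randomised groups, and that contrast is unbiased for the difference in change. Baseline values are needed only to describe loss within a child or to restrict attention to children who had a response at one year. Nor is chance imbalance at age one a separate harm. The unadjusted standard error already allows for it.

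The size of the gain rests on assumed values, and Sample size estimates already regards the cohort as probably large enough for the common outcomes and for large cytokine effects. This too stands. At 1170 per arm, with log-rate variance (1/μ₂ + k)/n in each arm and k from 0.25 to 1.0, the unadjusted contrast has 80% power for rate ratios of about 0.92 to 0.88. Adjustment moves these only to about 0.92 to 0.90. The count model's constant rate and constant child-level variation from infancy to age five are simplifications.

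Finally, a log-scale model needs care. Appendix 1 reports an assay limit of 8 pg/ml with background subtracted, and positive responses to the mycobacterial antigen in only 23% to 51% of its HIV-positive adults, by cytokine and helminth group. If children's data also contain many undetectable values, the assumed ρ may not carry over. That bears on how the fix is worded, but not on whether baseline carries information.

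**Conclusion.** The point holds as one of efficiency. For C1 versus C2, Appendix 4 names a post-randomisation variable and no pre-randomisation covariate, although suitable ones are collected before the first dose. No bias in the unadjusted contrast and no error in a stated figure follows from this.

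The benefit of adjustment is a variance reduction of 9% to 49% for immune responses if ρ is 0.3 to 0.7, and of about 10% to 39% for malaria and diarrhoea if between-child variance is 0.25 to 1.0. For pneumonia and tuberculosis it is negligible. Those ranges are assumptions, two-sided testing at 5% is assumed throughout, and the actual gain cannot be known from the protocol. The change is worth making because it is cheap and fixes the covariate in advance. That matters where Appendix 9 gives the principal investigator and project statisticians unblinded access for interim analyses.

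**What to change.** In the children's section of Appendix 4, specify that:

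- the primary Aim 3 analysis of BCG and tetanus responses is an analysis of covariance of the later response on arm and the same child's one-year response, on a log scale, with a stated rule for undetectable values and an indicator for a missing one-year value;
- a raw change score is not used as the primary analysis;
- malaria and diarrhoea incidence are compared by a rate model with the first-year episode count as covariate;
- the unadjusted C1 versus C2 contrast is reported as a sensitivity analysis.

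For pneumonia and tuberculosis no baseline count is needed.

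The cost is a few sentences of analysis text. No visit, sample or assay is added, since the one-year blood and first-year illness records are already planned. The only extra work is settling the rules for undetectable and missing baseline values before unblinded data are seen.
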